A by-subject listing of all AEs (including non-treatment-emergent events) will be provided. This listing will be presented by treatment group and will include: center, subject identifier, age, sex, race, AE (SOC, PT, and verbatim term), date of onset, date of resolution, duration, severity, seriousness, action taken, outcome and causality.

The following AEs are defined as AEs of special interest. Summaries of the number and percentage of subjects reporting the following AEs will be provided.

- PT: “hyperkalemia” (MedDRA 10020646) or “blood potassium increased” (MedDRA 10005725)
- PT: “hyperuricaemia” (MedDRA 10020903) or “blood uric acid level increased” (MedDRA 10022891)
- PT: “Hypertension” (MedDRA 10020772) or “Blood pressure increased” (MedDRA 10005750) or “Blood pressure systolic increased” (MedDRA 10005760) or “Blood pressure diastolic increased” (MedDRA 10005739) or “Blood pressure ambulatory increased” (MedDRA 10005732) or “Blood pressure inadequately controlled” (MedDRA 10051128) or “Accelerated hypertension” (MedDRA 10000358) or “Essential hypertension” (MedDRA 10015488) or “Diastolic hypertension” (MedDRA 10012758) or “Systolic hypertension” (MedDRA 10042957) or “Malignant hypertension” (MedDRA 10025600)

- Standardised MedDRA Query (SMQ): “Cholestasis and jaundice of hepatic origin” (SMQ 20000009) or “Drug related hepatic disorders – severe events only” (SMQ 20000007) or “Liver related investigations, signs and symptoms” (SMQ 20000008)
- Standardised MedDRA Query (SMQ): “Ischaemic heart disease” (SMQ 20000043)
- SMQ: “Central nervous system haemorrhages and cerebrovascular conditions” (SMQ 20000061)
- SMQ: “Embolic and thrombotic events” (SMQ 20000081)
- SMQ: “Cardiac failure” (SMQ 20000004)
- SMQ: “Retinal disorders” (SMQ 20000158, narrow)

Serious adverse events that occur during the screening period and are assessed by the investigator as related to study procedures will be tabulated separately from treatment-emergent serious adverse events.

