4.9.2 Treatment-Emergent Outliers analysis

The purpose of this analysis is to identify the treatment Emergent outliers by each prescribed dose at each period. The definition of prescribed doses is the subjects with latest dose amount at planned visit when dose change. e.g. if at Week 2 with dose 600 mg and dose reduced to 450 mg at week 4, then visit of prescribed dose for VADA 450 was assigned to Week 4.

However, if subject had dose reduction on 150 mg or had interruption of study medication, the prescribed dose will be considered as 0 mg.

Only treatment-emergent outliers will be counted but outliers at the baseline and screening visits will be excluded.

The following summary will be provided:

- The summary of subjects with prescribed Dose by treatment group and time point
- The summary of subjects with prescribed Dose by Above/Within/Below the target Hb Range and treatment group

In addition, the below components will be analyzed by primary efficacy period and dose adjustment and maintenance period for all subjects and for subjects with non-elevated values at baseline:

- Non-elevated at baseline definition for each component

- Systolic Blood Pressure <140 mmHg
- Diastolic Blood Pressure <90 mmHg
- Heart Rate <100 bpm
- Potassium <4 mEq/L

The following component with following criteria will be applied.

- Systolic Blood Pressure
 - Any SBP ≥ 160 to <180 mmHg
 - Any SBP ≥ 180 mmHg
 - Any SBP increase from baseline ≥ 20 to <40 mmHg
 - Any SBP increase from baseline ≥ 40 mmHg
- Diastolic Blood Pressure
 - Any DBP ≥ 100 to <110 mmHg
 - Any DBP ≥ 110 mmHg
 - Any DBP increase from baseline ≥ 10 to <20 mmHg
 - Any DBP increase from baseline ≥ 20 mmHg
- Heart Rate
 - Any pulse ≥ 100 to <120 bpm
 - Any pulse ≥ 120 bpm
 - Any pulse increase from baseline ≥ 20 to <30 bpm
 - Any pulse increase from baseline ≥ 30 bpm
- Potassium
 - Any Potassium >5.5 to 6.0 mEq/L
 - Any Potassium >6.0 to 6.5 mEq/L
 - Any Potassium >6.5 mEq/L
 - Any Potassium increase from baseline >0.5 to 1.0
 - Any Potassium increase from baseline >1.0 to 1.5 mEq/L
 - Any Potassium increase from baseline > 1.5 mEq/L

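### The <4 mEq/L cut-off for non-elevated baseline potassium lies 1.5 mEq/L below the first outlier limit, so that subgroup is poorly suited to showing new potassium outliers

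*SAP*

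**What the plan says.** SAP section 4.9.2 (Treatment-Emergent Outliers analysis) covers systolic and diastolic blood pressure, heart rate and potassium, by study period, "for all subjects and for subjects with non-elevated values at baseline". For potassium, non-elevated means "Potassium <4 mEq/L"; the parallel entry for systolic pressure is "Systolic Blood Pressure <140 mmHg".

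The lowest absolute potassium category is "Any Potassium >5.5 to 6.0 mEq/L", with two higher categories above 6.0 and above 6.5 mEq/L. The lowest change category is "Any Potassium increase from baseline >0.5 to 1.0" and the highest is "Any Potassium increase from baseline > 1.5 mEq/L".

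The section also states: "Only treatment-emergent outliers will be counted but outliers at the baseline and screening visits will be excluded".

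Neither document gives a reason for the value 4 or a potassium reference range. The SAP's own change log (section 6.1.3, Change#24) carries the same figure, so it is unlikely to be a fault in the text extraction.

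**The concern.** A subgroup labelled non-elevated would be expected to hold the subjects who start below the range the plan treats as abnormal, so that anyone who later enters that range is visibly new. For potassium the label and the limits do not meet. A baseline anywhere from 4.0 to 5.5 mEq/L lies below every absolute outlier limit, yet it fails the non-elevated definition. These are the subjects who can cross 5.5 with a small or moderate rise, and the subgroup leaves them out. Those who remain must rise a long way before any absolute category registers them.

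Potassium matters enough to this plan that hyperkalaemia, together with "blood potassium increased", is an adverse event of special interest (SAP section 4.8.2). A subgroup table with empty absolute rows could be taken as evidence that subjects with unremarkable potassium at entry did not develop high values, when the cut-off itself made such rows hard to fill.

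**Working it through.** **Inputs.** All limits come from SAP section 4.9.2. Under SAP section 4.2, the pre-treatment value for variables other than Hb is the last available one before treatment, in general the baseline visit.

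**Formula.** Gap = first absolute outlier limit − baseline cut-off. The gap is then compared with the lower bounds of that component's own lowest and top increase categories.

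| Component | Baseline cut-off | First outlier limit | Gap | Lowest increase bound | Gap ÷ lowest | Top increase bound | Gap ÷ top |
|---|---|---|---|---|---|---|---|
| Systolic BP (mmHg) | <140 | ≥160 | 20 | 20 | 1 | 40 | 0.5 |
| Diastolic BP (mmHg) | <90 | ≥100 | 10 | 10 | 1 | 20 | 0.5 |
| Heart rate (bpm) | <100 | ≥100 | 0 | 20 | 0 | 30 | 0 |
| Potassium (mEq/L) | <4 | >5.5 | 1.5 | 0.5 | 3 | 1.5 | 1.0 |

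Potassium is the only component whose gap reaches its top increase category.

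**Smallest possible rise.** Both potassium limits are strict, so the rise must exceed 1.5 mEq/L. With values reported to 0.1 the smallest case is 3.9 to 5.6, a rise of 1.7. With values reported to 0.01 it is 3.99 to 5.51, a rise of 1.52. Every absolute outlier in the subgroup is therefore also counted in the >1.5 row.

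**Other cut-offs.** The rise needed to pass 5.5 mEq/L is:

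- <4.0: more than 1.5
- <4.5: more than 1.0
- <5.0: more than 0.5, one lowest step, as for systolic and diastolic pressure
- ≤5.5: more than 0, as for heart rate

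**Size of the subgroup (assumption).** The documents give no baseline potassium distribution. Taking it as normal with SD 0.5 to 0.9 mEq/L, the share below 4 depends mainly on the mean:

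| Assumed mean (mEq/L) | Share <4 | Per 12 subjects |
|---|---|---|
| 4.0 | 50% | 6.0 |
| 4.5 | 15.9% to 28.9% | 1.9 to 3.5 |
| 5.0 | 2.3% to 13.3% | 0.3 to 1.6 |
| 5.5 | 0.1% to 4.8% | 0.0 to 0.6 |

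Twelve is the planned group size (SAP section 4.10). The gap arithmetic does not depend on this table.

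**The case against.** The strongest reply is that the subgroup is not the plan's only view of potassium. Section 4.9.2 runs the same categories for all subjects and keeps outliers seen at screening or baseline out of the count. A subject who moves from 4.0–5.5 to above 5.5 is therefore recorded there. The special-interest adverse event summary (4.8.2), the potassium values, changes and by-subject listing (4.8.4.7) and the CTCAE abnormality table (4.8.4.9) do not use the cut-off. All of this stands. A reader might infer that the trial could miss a potassium signal; the documents do not support that.

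A reader might also infer that the absolute categories become redundant within the subgroup. They do not. The implication runs one way: a rise from 3.0 to 4.8 is in the top increase category without being an absolute outlier. The absolute rows therefore still separate large rises that pass 5.5 from those that do not, and they grade the level reached. The two lower increase categories still register smaller rises.

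Finally, the SAP nowhere requires a baseline cut-off to sit within one increase step of the first outlier limit, and the three comparators do not share one rule (one, one and zero steps). That is fair: the comparison shows that potassium is out of line but does not prove a mistake. It still leaves unexplained why values of 4.0 to 5.5 mEq/L fail a non-elevated definition when the plan's outlier range begins above them.

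**Conclusion.** The point holds within narrow bounds. In the subgroup, an absolute potassium outlier requires a rise of more than 1.5 mEq/L, three lowest increase steps, against one, one and zero for the other three components. All subjects with baseline 4.0 to 5.5 mEq/L are excluded from it. The subgroup is therefore poorly suited to showing new potassium outliers, and sparse or empty absolute rows should not be read as reassurance.

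This follows exactly from the limits in section 4.9.2 and needs no outside reference range. How many subjects it affects is unknown, because that depends on a baseline distribution the documents do not give.

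The analysis is descriptive safety. The primary endpoint, type I error control, power and study conduct are untouched. The documents do not show whether <4 is a slip or a deliberate choice, so calling it a typing error would go too far.

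**What to change.** In SAP section 4.9.2, replace <4 mEq/L with a cut-off that fits the plan's own categories. Two options do so:

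- <5.0 mEq/L, one 0.5 step below the first outlier limit, which reproduces the blood pressure pattern.
- At or below the central laboratory's upper limit of normal. The documents do not state this value, so the SAP would need to cite it.

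A cut-off of ≤5.5 mEq/L is less useful. If the exclusion rule removes subjects already above 5.5 at baseline, the subgroup would largely repeat the all-subjects absolute counts.

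Keep the outlier categories and the all-subjects analysis as they are. If <4 is deliberate, give the reason and drop the non-elevated label for potassium.

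The cost is one cut-off in the SAP and in the table program, with no new data.

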4.10 Determination of Sample Size

The target enrollment will be approximately 48 subjects for the study with around 12 subjects enrolled in each of the 4 treatment groups.

The study is powered based on a comparison of the highest dose vadadustat group (600 mg daily) and the placebo group. Based on the results from Study AKB-6548-CI-0005 that was conducted in the United States and evaluated vadadustat in patients with anemia secondary to DD-CKD, it is assumed that the expected mean Hb changes from baseline to Week 6 will be approximately 0 mg/dL for the placebo group and 1.35 g/dL for the highest dose vadadustat group (600 mg daily), with a common standard deviation of 0.68 g/dL across treatment groups. With these assumptions, the study with n=12 subjects per group will have >95% power to detect the difference between treatment group and control group, at 2-sided alpha of 0.05.

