## 11.2 Primary Efficacy Analysis and Sample Size Determination

An analysis of covariance (ANCOVA) model will be used to compare change from pre-treatment in Hb between the three vadadustat dosing groups and the placebo group. The model will include treatment assignment (3 dosed groups and one placebo group) and pre-treatment Hb value as a covariate. A step-down procedure will be used to control the overall type I error rate for the multiple comparisons. Testing of the highest dose compared with placebo will be conducted first. If and only if this comparison is significant, then testing will proceed to comparison of the next lower dose and placebo, and so on. Thus, no multiplicity adjustment will be needed for this analysis.

The sample size and power calculations are based on results from Study AKB-6548-CI-0005 that was conducted in the United States and evaluated vadadustat in patients with anemia secondary to non-dialysis-dependent CKD. It is reasonable to extrapolate these data to the current study based on the following findings:

- PK parameters of vadadustat are similar between CKD patients who are receiving hemodialysis (Study AKB-6548-CI-0009) and CKD patients who are not receiving dialysis (Study AKB-6548-CI-0003)
- Hemodialysis procedure has no significant impact on the PK of vadadustat (Study AKB-6548-CI-0009)
- The dose range of 150-600 mg of vadadustat to be used in the current study has been shown to be generally well-tolerated, and efficacious in raising and/or maintaining Hb at the desired target level in CKD patients who were either on hemodialysis (Study AKB-6548-CI-0011) or CKD patients who were not on dialysis (Studies AKB-6548-CI-0005 and AKB-6548-CI-0007)

The target enrollment will be approximately 48 subjects for the study with 12 subjects enrolled in each of the 4 treatment groups.

The study is powered based on a comparison of the highest dose vadadustat group (600 mg daily) and the placebo group.

Based on the results from Study AKB-6548-CI-0005 that was conducted in the United States and evaluated vadadustat in patients with anemia secondary to NDD-CKD, it is assumed that the expected mean Hb changes from pre-treatment to Week 6 will be approximately 0 mg/dL for the placebo group and 1.35 g/dL for the highest dose vadadustat group (600 mg daily).

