Based on the results from Study AKB-6548-CI-0011 that was conducted in the United States and evaluated vadadustat in patients with anemia secondary to DD-CKD, it is assumed that the common Hb standard deviation will be 0.9 g/dL across treatment groups. In addition, a dropout rate of 10% is assumed. With these assumptions, the study with n=12 subjects per group will have >85% power to detect the difference between treatment group and control group, at 2-sided alpha of 0.05.

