## NOTE TO FILE

---

**Protocol Number:** AKB-6548-CI-0022

**Protocol Title:** Phase 2, Randomized, Double-Blind, Placebo-Controlled, Dose-Finding Study to Assess the Efficacy, Safety, Pharmacokinetics, and Pharmacodynamics of Vadadustat in Japanese Subjects with Anemia Secondary to Dialysis Dependent Chronic Kidney Disease

**Subject:** Administrative errors in Protocol Version 2.0 and Summary of Changes (SOC)

**Date:** 03 February 2017

---

This is to clarify that the following administrative errors were noted in Protocol version 2.0 and the corresponding Summary of Changes (SOC) document, dated 23 November 2016.

- **The following highlighted text the protocol synopsis, protocol section 11.2, and the SOC, is incorrect: “mg/dL” should be “g/dL”**
  - *Based on the results from Study AKB-6548-CI-0005 that was conducted in the United States and evaluated vadadustat in patients with anemia secondary to NDD-CKD, it is assumed that the expected mean Hb changes from baseline to Week 6 will be approximately 0 mg/dL for the placebo group and 1.35 g/dL for the highest dose vadadustat group (600 mg daily), with a common standard deviation of 0.68 g/dL across treatment groups.*

**Printed Name:** \_\_\_\_\_ **Role:** Clinical Project Manager \_\_\_\_\_

**Signature:** \_\_\_\_\_ **Date:** \_\_\_\_\_

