1 INTRODUCTION

This study is a Phase 2 clinical study to assess the dose-response relationship between oral vadadustat once daily dosing for 6 weeks and the change in hemoglobin (Hb) in Japanese subjects with anemia secondary to dialysis dependent chronic kidney disease (DD-CKD); in order to define the starting dose for use in Phase 3 clinical studies in Japan.

This Statistical Analysis Plan (SAP) defines the preliminary and final statistical analyses for the clinical study report for this study. This should be read in conjunction with the study protocol that provides all necessary background information and rationale for the current study and its design.

The pharmacokinetic data will be separately obtained from vendor to keep blindness of the study.

This SAP is based upon the following study documents:

- Study Protocol, Version 2 (November 23, 2016)
- electronic Case Report Form (eCRF), Version 2.0 (January 27 2017)
- Protocol Deviation Specification Form, Version 2.0 (February 07, 2017)

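### SAP 4.10 claims more than 95% power using an SD and dropout rate that Protocol Version 2 had replaced; on the protocol's inputs power is about 89 to 94%, depending on method

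*SAP*

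**What the plan says.** SAP section 1 lists Protocol Version 2 of 23 November 2016 among the documents it is built on. The two sample-size sections then differ:

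| Item | SAP 4.10 | Protocol 11.2 (same in the synopsis) |
|---|---|---|
| Difference, 600 mg vs placebo | 1.35 g/dL | 1.35 g/dL |
| Number per group, alpha | 12, two-sided 0.05 | 12, two-sided 0.05 |
| Common SD | 0.68 g/dL, attributed to CI-0005 | 0.9 g/dL, from CI-0011 |
| Dropout | none stated | 10% |
| Population of CI-0005 | dialysis-dependent | non-dialysis-dependent |
| Reference for change | baseline | pre-treatment |
| Power | >95% | >85% |

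The SAP's claim is that "the study with n=12 subjects per group will have >95% power to detect the difference between treatment group and control group". The protocol's text reads "it is assumed that the common Hb standard deviation will be 0.9 g/dL across treatment groups", and it goes on: "a dropout rate of 10% is assumed. With these assumptions, the study with n=12 subjects per group will have >85% power". On CI-0005, the SAP says it "evaluated vadadustat in patients with anemia secondary to DD-CKD", and the protocol says it "evaluated vadadustat in patients with anemia secondary to NDD-CKD".

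The note to file of 3 February 2017 was issued to correct a unit (mg/dL to g/dL). The sentence it reproduces as protocol text ends "with a common standard deviation of 0.68 g/dL across treatment groups". That phrase is not in Protocol 11.2.

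**The concern.** The SAP and the protocol it rests on give different variability, dropout and power for the primary comparison, and nothing in the SAP accounts for this. Section 4.11 declares no changes to the planned analysis, and none of the changes listed in SAP Amendment 1 touches 4.10. The protocol's own summary of changes shows that moving to 0.9 g/dL and 10% dropout was deliberate: the SD was raised to suit the dialysis population, and the stated power came down from >95% to >85%.

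Two things are at stake. A study report that follows the SAP would state a power the design does not have under its agreed assumptions. And calling CI-0005 a dialysis study means a reader of 4.10 would not see that the 1.35 g/dL effect is borrowed from non-dialysis patients, an extrapolation the protocol states and defends.

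**Working it through.** **Inputs.** Difference 1.35 − 0 = 1.35 g/dL, 12 per group and two-sided alpha 0.05 (both documents). SD 0.68 with no dropout (SAP 4.10). SD 0.9 with 10% dropout (Protocol 11.2).

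**Method.** For n evaluable per arm, the noncentrality is δ = 1.35 / (SD × √(2/n)). Power is the probability that a noncentral t variable with that δ exceeds the two-sided 5% critical value. I used error df 2n − 2 (two-sample t-test) and 4n − 5 (four-group ANCOVA with one covariate, no reduction in SD credited). The normal approximation is Φ(δ − 1.96). Neither document says which method it used.

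**Step 1: the SAP's own figure.** δ = 1.35 / (0.68 × √(2/12)) = 4.86, df 22. Power is 99.6% by t-test and 99.8% by the normal approximation. The claim of >95% holds on these inputs.

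**Step 2: the protocol's inputs.** Ten per cent dropout leaves 12 × 0.9 = 10.8 per arm, which I bracket with 10 and 11. At 10.8, δ = 1.35 / (0.9 × √(2/10.8)) = 3.49.

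| Evaluable per arm | t-test | ANCOVA df | Normal approximation |
|---|---|---|---|
| 10 | 88.7% | 90.3% | 91.8% |
| 10.8 | 91.2% | 92.5% | 93.6% |
| 11 | 91.7% | 92.9% | 94.0% |
| 12 (no dropout) | 93.9% | 94.9% | 95.7% |

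The protocol's >85% reproduces in every row. With the protocol's dropout, no entry reaches 95%. By t-test, the chance of missing a true 1.35 g/dL effect is about 8 to 11% (100 − 91.7 to 100 − 88.7), against under 5% as the SAP states and 0.4% on the SAP's inputs.

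**Step 3: which inputs differ.** The effect, n and alpha agree. The SD and dropout are the replaced values. The dialysis label for CI-0005 is a separate error: the replaced protocol text also called it a non-dialysis study. The reference to baseline conflicts with the SAP's own primary endpoint in sections 2.1 and 4.7.2, which is change from the pre-treatment average.

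**The case against.** The best case against is that this is a text mismatch with no consequence. Neither document miscalculates, no planned estimate or test uses 0.68, and the protocol itself says the change in assumptions does not affect study conduct. All of that is true. It means the fault lies in the inputs and that the design need not change; it does not make the SAP's power statement right. Likewise, the non-dialysis source of the effect is disclosed in the protocol, which the SAP asks to be read alongside it, so the SAP misdescribes the source rather than conceals it.

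The second argument is that 95% might be reached after all. If 0.9 is an unadjusted SD, adjusting for pre-treatment Hb helps: with 10.8 per arm and ANCOVA df, power is 93.4%, 94.5% and 96.0% for assumed correlations of 0.2, 0.3 and 0.4. LOCF (SAP 4.7.1.3) also keeps dropouts who have an eligible on-treatment Hb; if none were lost, SD 0.9 gives 93.9 to 95.7%. These results are correct but conditional. No correlation is given in either document, neither sample-size section credits LOCF, and a value carried forward from Week 2 or 4 probably understates the Week 6 effect.

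The third point, that 89 to 92% is only the t-test range, stands. Across the three methods the range is about 89 to 94%.

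**Conclusion.** The concern holds. SAP 4.10 claims more than 95% power on an SD and dropout rate that Protocol Version 2 had replaced, and it misidentifies the population behind the effect size. On the protocol's assumptions (difference 1.35 g/dL, SD 0.9 g/dL, 10% of subjects lost, no precision gain from the covariate) power is 88.7 to 91.7% by t-test, 90.3 to 92.9% with four-group ANCOVA df, and 91.8 to 94.0% by the normal approximation. Reaching 95% requires a further assumption that neither document states. The protocol's >85% is supported, so 12 per group and the primary test need not change.

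**What to change.** Replace SAP 4.10 with the assumptions of Protocol 11.2:

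- difference 1.35 g/dL from CI-0005, identified as a non-dialysis study;
- SD 0.9 g/dL from CI-0011, the dialysis study;
- 10% dropout;
- change measured from pre-treatment;
- placebo change of 0 g/dL (4.10 still has mg/dL, the unit error the note to file corrected for the protocol);
- power >85%.

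If a point figure is wanted beside the >85%, name the method and the evaluable number, since the result moves by several percentage points with both. Reissue the note to file of 3 February 2017 so that it quotes the actual Version 2 sentence without 0.68.

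The cost is one SAP paragraph, an entry in the SAP change record and a corrected note. The stated power becomes less favourable; sample size, endpoint and analysis are unaffected.
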